9.2 Sample Size

Sample size considerations were based on monitoring the primary efficacy endpoint, ORR, using a 2-arm Bayesian optimal phase 2 (BOP2) design (Zhao et al 2022).

Specifically, let n denote the interim sample size and N denote the maximum sample size. Let ORR_{con} denote the control ORR and ORR_{comb} denote the combination treatment ORR. We define the null hypothesis $H_0: ORR_{comb} \leq ORR_{con}$, under which the combination arm is deemed as unacceptable, respective to the control. We employ the following Bayesian rule to make a go/no-go decision:

(Futility stopping) stop enrolling patients and claim that the experimental arm is unacceptable if:

$$Pr(ORR_{comb} > ORR_{con} | data) < \lambda \left(\frac{n}{N}\right)^\alpha,$$

Where $\lambda=0.96$ and $\alpha=0.94$ are design parameters optimized to maximize the power under $H_0: ORR_{con} = 0.15$ and $ORR_{comb} = 0.43$, while controlling the type I error rate at 0.05 under $ORR_{con} = ORR_{comb} = 0.15$. This optimization is performed assuming a vague prior Beta(0.5,0.5) for ORR_{con} and ORR_{comb} .

An interim futility analysis is planned when ORR can be assessed for the first 39 patients, and the final ORR analysis is planned after 81 patients are followed for a minimum of 3 months (2 radiologic scans). A 2:1 combination:control randomization will be used for the 2 arms and will yield 83% power at the 1-sided 5% alpha based on the above decision rule to reject the null hypothesis and conclude that the combination arm is superior compared to the control:

At the interim analysis: $Pr(ORR_{comb} > ORR_{con} | data) > 0.5$, and

At the final analysis: $Pr(ORR_{comb} > ORR_{con} | data) > 0.96$

The go/no-go criteria, also presented in detail in Table 9 below, are non-binding.

The operating characteristics of the design, based on 100000 simulations using the BOP2 application, are presented in Table 10.

Table 9: Optimized Stopping Boundaries

Control N	Combination N	# CR/PR in Control	Stop for Futility if # of CR/PR in Combination - # of CR/PR in Control ≤
13	26	0	0
13	26	1~2	1
13	26	3	2
13	26	4	3
13	26	5	4
13	26	6	5
13	26	7	6
13	26	8	7
13	26	9	8
13	26	10	9
13	26	11	10
13	26	12	11
13	26	13	12
27	54	0	4
27	54	1	7
27	54	2	10
27	54	3	11
27	54	4	13
27	54	5	15
27	54	6	16
27	54	7	17
27	54	8	18
27	54	9	20
27	54	10	21
27	54	11	22
27	54	12~13	23
27	54	14	24
27	54	15	25
27	54	16~17	26
27	54	18~19	27
27	54	20~26	28
27	54	27	27

Abbreviations: CR = complete response; PR = partial response

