9.7 Analysis of Efficacy

The primary efficacy analysis for ORR, as well as the interim analysis for PFS and OS, will be conducted once all patients are treated and followed for a minimum of 3 months (2 radiologic scans). The final analysis for PFS and OS will be conducted after all patients have been followed for a minimum of 15 months, unless the study is deemed futile at the interim or primary analysis stage.

The overall response will be assessed by the Investigator based on the RECIST v1.1 criteria at each timepoint specified the SoA ([Section 8.1](#)). The best overall response (BOR) will be assessed from response assessments occurring after the first dose of either study treatment up to the first documented assessment of PD that is prior to the initiation of a new anticancer therapy. Objective response (i.e., BOR of PR or CR) will require confirmation of the response (CR or PR) at least 4 weeks after the initial CR or PR.

The ORR will be defined as the proportion of patients with a confirmed objective response as assessed by the Investigator in the FAS. Patients who receive at least one dose of either study treatment but have no valid postbaseline radiographic assessment will be considered non-responders. The ORR will be reported along with the corresponding 2-sided 90% and 95% Clopper-Pearson exact CI. The criteria for promising ORR at the primary analysis are detailed in [Table 9](#) and, in addition, a comparison between the 2 treatment groups will be performed based on Fisher's exact test.

DOR is defined as the date of the patient's first confirmed BOR of CR or PR to the earliest date of documented progression or death if no prior evidence of disease progression, for all patients in the FAS with a confirmed objective response. A patient that starts a new anticancer therapy prior to disease progression will be censored at the date of last valid disease assessment prior to the start of the new anticancer therapy. All other patients without progression or death will be censored at the date of the last valid disease assessment. DOR will be summarized using Kaplan-Meier methods.

The DCR, which includes a BOR of CR, PR, or SD, will be analyzed similar to ORR.

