#### 5.12.4.2 Duration of Response

Duration of response (DOR) is defined as the date of the patient's first BOR of CR or PR to the earliest date of documented progression or to death if no prior evidence of disease progression. DOR will be calculated as follows for all patients in the FAS population with a confirmed objective response. The date of the first confirmed response is based on the first instance of CR or PR that is confirmed by repeat assessments at least 4 weeks later.

QMD Ref: Worldwide-TMP-ST-054-1.0_Effective: 12Aug2022	Governing QMD: Worldwide-SOP-ST-026
Confidentiality Statement	
This document is the property of Worldwide Clinical Trials Inc. and may not be duplicated, copied, altered or removed from company without prior approval from Worldwide Quality Assurance or in compliance with Worldwide Standard Operating Procedures.	

Worldwide Clinical Trials Controlled Quality Management Document			
 WORLDWIDE CLINICAL TRIALS	Sponsor:	Flamingo Therapeutics	
	Protocol Number:	FLM-6774-201	
STATISTICAL ANALYSIS PLAN			

$$DOR \text{ (Months)} = \frac{(Date \text{ of } PD, \text{Death, or censoring} - Date \text{ of } 1^{\text{st}} \text{ confirmed CR or PR}) + 1}{30.4375}$$

DOR may be censored to a stop date other than PD or death, as described in the censoring rule table of [Section 5.12.4.5](#).

Kaplan-Meier estimates of 25th, 50th and 75th percentiles for DOR will be presented. Corresponding 95% confidence intervals using Greenwood's formula will be provided. Minimum and Maximum DOR will be presented.

The following SAS code will be used.

```
proc lifetest data=adtte timelist=3 6 9 12 reduceout outsurv=<outdata>;
  time aval*cnsr(1);
  by trt01pn;
run;
```

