#### 5.12.4.5 Censoring Rules for Time-to-Event Parameters

Progression-Free Survival and Duration of Response Censoring			
#	Event Description	Stop Date Used	Outcome
1	Documented radiological PD before initiation of non-study anti-cancer treatment	Date of the first tumor assessment that determined PD	Event
2	Death during the study with no prior PD and no prior initiation of non-study anti-cancer treatment	Date of death	Event
3	Radiographic PD or death after a missed (or not available / not evaluable) tumor response assessment**	Date of last adequate tumor assessment prior to missed tumor assessment	Censored
4	Patient administered new anticancer therapy prior to disease progression	Date of last valid disease assessment prior to start of new anticancer therapy	Censored
5*	No evaluable post-Baseline tumor assessment	Date of first dose	Censored
6*	Patient without documented progression or death	Date of the last valid disease assessment date	Censored
7*	Patient withdrawal or lost to follow-up	Date of the last valid disease assessment	Censored
Overall Survival Censoring			
#	Event Description	Stop Date Used	Outcome
1	Death from any cause	Date of death	Event
2	Patient withdrawal or lost to follow-up	Date of the last contact	Censored
3	Patient without documentation of death as of the data cutoff	Date of last contact where subject known to be alive.	Censored

\*Not applicable to Duration of Response

\*\*A tumor response assessment is considered missed if more than 13 weeks (91 days) has elapsed since the last image-based tumor response assessment. If a subject develops progressive disease or dies directly after this interval, the tumor response assessment will be excluded from analysis and censored to the last evaluable assessment. However, if a response assigned as CR, PR, or SD is obtained after more than 13 weeks, then the tumor response will not be excluded.

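### The SAP's censoring table gives responders who are still in response no DOR censoring date, contradicting the protocol and biasing DOR downward if programmed as written

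*SAP*

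**What the plan says.** SAP 5.12.4.2 defines the DOR population: "DOR will be calculated as follows for all patients in the FAS population with a confirmed objective response". Its formula has a censoring term, but it gives no censoring rule of its own. It says only that "DOR may be censored to a stop date other than PD or death, as described in the censoring rule table of" Section 5.12.4.5.

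That table serves PFS and DOR together. Rows 5, 6 and 7 are asterisked, and the footnote reads "Not applicable to Duration of Response". The rows are:

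- Row 5: no evaluable post-baseline assessment.
- Row 6: "Patient without documented progression or death", censored at the last valid disease assessment.
- Row 7: "Patient withdrawal or lost to follow-up", censored at the same date.

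The rows left for DOR are progression (row 1), death (row 2), progression or death after a missed assessment (row 3), and row 4, "Patient administered new anticancer therapy prior to disease progression".

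Protocol 9.7 has its own DOR rule. After dealing with new anticancer therapy it says: "All other patients without progression or death will be censored at the date of the last valid disease assessment". SAP Section 9, which lists changes to the protocol analysis, mentions only that the final analysis comes early because the study was terminated.

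**The concern.** A responder who is alive, progression-free and on no new therapy at cut-off fits none of rows 1 to 4, so the SAP supplies no stop date. The DOR formula then returns a missing value, and PROC LIFETEST leaves out records with a missing time. What remains is responses that have ended, plus the few censored under rows 3 and 4. Kaplan-Meier estimation needs the ongoing responses as censored observations; without them the analysis is conditional on having failed during follow-up.

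DOR is a secondary endpoint overall and in CPS ≥20 and ≥50. It is also tabulated by subgroup and in the interim report. The distortion is largest in the arm with the more durable responses, and early termination is likely to leave more responses ongoing.

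**Working it through.** **1. Which rows give a DOR stop date**

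| Status of a confirmed responder | SAP table, DOR | Protocol 9.7 |
|---|---|---|
| Progressed or died | Rows 1 and 2, event | Event |
| Progressed or died after a missed assessment | Row 3, censored | No separate rule |
| New therapy before progression | Row 4, censored | Censored at last valid assessment before it |
| Still in response at cut-off | None (row 6 excluded) | Censored at last valid assessment |
| Withdrawn or lost, no progression or death | None (rows 6 and 7 excluded) | Censored at last valid assessment |

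**2. Number of responders**

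The documents give no sample size or event count for DOR; the only design figure is for ORR. Exact enumeration of the two-stage rule (Beta(0.5, 0.5) priors, λ = 0.96, α = 0.94, 13/26 patients at the interim and 27/54 at the end) gives 82.6% power at 0.15 versus 0.43. Protocol Table 10 states 82.7%, so the design reproduces. At those rates DOR would rest on 54 × 0.43 = 23.2 combination responders and 27 × 0.15 = 4.05 control responders.

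**3. Direction**

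Let D be the true duration and C the follow-up after response, independent of D. A response of length d is retained with probability P(C ≥ d), which falls as d rises. Retained responses are therefore systematically shorter, whatever the shape of D.

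**4. Size**

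Protocol 1.1.2 gives a DOR of 42 weeks in the earlier combination study. It is taken here as an exponential median, which is an assumption: 42 × 7 / 30.4375 = 9.66 months, so the rate is ln 2 / 42 = 0.0165 per week.

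If follow-up after response is uniform on (a, b) weeks, the ongoing fraction is [exp(−0.0165a) − exp(−0.0165b)] / [0.0165(b − a)].

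- a = 4, b = 52: (0.936 − 0.424) / 0.792 = 0.65.
- a = 55, b = 110: (0.404 − 0.163) / 0.908 = 0.265.

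Simulation with 23 responders and 4,000 replicates gave these medians:

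- 4 to 52 weeks: about 43 weeks with the protocol's censoring, about 13 weeks with ongoing responders dropped.
- 55 to 110 weeks: about 42 and 28 weeks.

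A second simulation (200,000 responders) used the planned minimum follow-up of 3 months (primary analysis) and 15 months (final PFS/OS analysis). It assumed response at week 6 or 12 and uniform accrual over 12, 18 or 24 months, which the documents do not give. It applied no rounding to scan dates and no row 3 or 4 censoring.

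| Minimum follow-up | Accrual (months) | Ongoing | Median, protocol rule (months) | Median, dropped (months) | 12-month rate, protocol rule / dropped | Combination responders kept, of 23.2 |
|---|---|---|---|---|---|---|
| 3 months | 12 | 63% | 9.7 | 3.1 | 0.42 / 0.00 | 8.6 |
| 3 months | 18 | 53% | 9.7 | 4.1 | 0.42 / 0.07 | 11.0 |
| 3 months | 24 | 45% | 9.6 | 4.9 | 0.42 / 0.14 | 12.8 |
| 15 months | 12 | 27% | 9.7 | 6.4 | 0.42 / 0.22 | 17.0 |
| 15 months | 18 | 22% | 9.7 | 6.9 | 0.42 / 0.26 | 18.0 |
| 15 months | 24 | 19% | 9.6 | 7.3 | 0.42 / 0.29 | 18.8 |

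**The case against.** **The SAP never says to drop ongoing responders.** Section 5.12.4.2 includes every confirmed responder, its code reads a censoring flag, and the protocol supplies the missing date. The asterisks on rows 6 and 7 may well be a drafting slip. This is fair: the defect is a contradiction with an answer at hand. But the footnote is explicit and Section 5.12.4.2 sends the programmer to that table. The DOR tables are validated by independent programming, so one programmer following the table and another following the protocol would disagree.

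**Row 7 is partly redundant.** Once row 6 applies, it already covers a withdrawn or lost responder with no progression or death. Sites must still trace survival after withdrawal, so a later death could fall under both row 2 and row 7. That overlap exists for PFS already, and row 7 uses the same date as row 6. It calls for a precedence statement but does not justify keeping the asterisk.

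**The sizes are assumption-bound.** With 23 responders and 4 to 52 weeks' follow-up, the correct median is not reached in about 42% to 44% of replicates. The 43 weeks counts those as infinite; where reached, the median averages about 34 weeks. If 10% to 30% of responses ended in new therapy (an assumption), row 4 censoring would raise 13 and 28 weeks to about 14–16 and 29–32. Those two figures also sit at the severe end of the range in the table. The protocol does not call 42 weeks a median, and 23 responders presumes full enrolment in a study that stopped early. All of this qualifies the size.

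**The stakes are limited.** DOR is compared descriptively with no between-arm test, and about four control responders would make any contrast weak. This stands.

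**Conclusion.** The concern holds. As written, the SAP gives no DOR censoring date to a responder who is still in response, withdrawn or lost, which contradicts Protocol 9.7 without being declared as a change. If the table is programmed literally, DOR is biased downward. Under an exponential DOR with a 9.7-month median and 12 to 24 months' accrual, the reported median would be 3.1 to 4.9 months at 3 months' minimum follow-up, or 6.4 to 7.3 months at 15 months. At an early cut-off a median that should be reported as not reached could also appear as a short finite value. The direction requires only that follow-up be independent of duration. The ORR decision, PFS and OS are unaffected, so this should be corrected but does not threaten the primary analysis.

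**What to change.** Remove the asterisk from rows 6 and 7 of the table in SAP 5.12.4.5 and keep it on row 5. Responders without progression, death or new therapy are then censored at the last valid disease assessment, as in Protocol 9.7. It would help to add that row 7 applies only where no progression or death is documented, which also settles the overlap with row 2 for PFS. The cost is two asterisks and, optionally, one clause. No new data, visits or patients are needed. Any DOR program already written from the table should be checked against the corrected rule.

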#### 5.12.5 Sensitivity Analysis

Sensitivity analysis will be conducted to evaluate the effect of requiring a confirmed objective response for ORR and DOR derivations. The sensitivity analyses for ORR and DOR will be the same as performed for the primary and secondary efficacy analyses, except confirmation of CR and PR by repeat assessments will not be required.

QMD Ref: Worldwide-TMP-ST-054-1.0_Effective: 12Aug2022	Governing QMD: Worldwide-SOP-ST-026
Confidentiality Statement	
This document is the property of Worldwide Clinical Trials Inc. and may not be duplicated, copied, altered or removed from company without prior approval from Worldwide Quality Assurance or in compliance with Worldwide Standard Operating Procedures.	

Worldwide Clinical Trials Controlled Quality Management Document			
 WORLDWIDE CLINICAL TRIALS	Sponsor:	Flamingo Therapeutics	
	Protocol Number:	FLM-6774-201	
STATISTICAL ANALYSIS PLAN			

## 5.12.6 Subgroup Analyses

Subgroup analyses will be performed for the primary and secondary efficacy endpoints for the FAS population. This includes analysis for ORR, DOR, PFS, and OS. The following subgroups will be used.

- Baseline Combined Positive Score Category (CPS < 20, CPS >= 20)
- Sex at Birth (Male, Female)
- Age Group (< 65, >=65)
- ECOG PS (0, 1)
- HPV Status (Positive, Negative)
- Region (US, Non-US)

For subgroup analysis of PFS by Baseline CPS category, Baseline CPS category will be removed as a stratification factor from the Cox Proportional Hazard Model. All subgroup analyses are considered descriptive, and no hypothesis testing will be performed.

## 5.12.7 Multiplicity

All secondary endpoints and these supportive analyses will be considered as descriptive evidence of efficacy and will be analyzed without any procedures to account for multiple comparisons.

## 5.12.8 Additional Efficacy Plots

Supportive efficacy data will be plotted for the FAS based on planned treatment.

A forest plot will be provided, presenting the risk difference between treatment arms for ORR and DCR, by Baseline CPS, Baseline ECOG, sex at birth, age group, and overall. Forest plots for PFS and OS will also be provided to present the hazard ratio between combination arm to Pembrolizumab, by the same subgroups.

A waterfall plot presenting the best percent change from baseline in sum of target lesions (mm) will be provided. Each bar will represent one subject and will be color-coded based on that subject's BOR.

A spider plot presenting the percent change from baseline in the sum of target lesions (mm) versus time (analysis visits) will be provided. Each line path will represent one subject and will be color-coded based on the subject's BOR.

A Swimmer's plot for duration of treatment (months) by subject will be provided, presenting overall response at each visit. Each bar will be color-coded by BOR.

QMD Ref: Worldwide-TMP-ST-054-1.0_Effective: 12Aug2022	Governing QMD: Worldwide-SOP-ST-026
Confidentiality Statement	
This document is the property of Worldwide Clinical Trials Inc. and may not be duplicated, copied, altered or removed from company without prior approval from Worldwide Quality Assurance or in compliance with Worldwide Standard Operating Procedures.	

Worldwide Clinical Trials Controlled Quality Management Document			
 WORLDWIDE CLINICAL TRIALS	Sponsor:	Flamingo Therapeutics	
	Protocol Number:	FLM-6774-201	
STATISTICAL ANALYSIS PLAN			

## 5.13 Safety Analyses

All safety analyses will be presented by actual treatment for the Safety Analysis Set.

### 5.13.1 Adverse Events

Treatment-emergent adverse events (TEAE) are reported according to protocol as any AE that has an onset on or after the first dose of study drug or any pre-existing condition that has worsened on or after the first dose of study drug up to the subject completion of the study.

A treatment-related AE is defined as an AE as being definitely, possibly, or probably, related to the study drug.

All TEAE summaries will include the number and percentage of subjects experiencing each adverse events as well as the total number of events. The following TEAEs will be summarized separately by system organ class and preferred term, as coded by MedDRA dictionary.

- Any TEAE
- Any TEAE (PT only)
- Related to Any Study Treatment
- Related to Danvatirsen
- Serious
- Serious Related to Any Study Drug
- Leading to Discontinuation of All Study Drugs
- Leading to Discontinuation of Danvatirsen only
- Leading to Discontinuation of Pembrolizumab only
- Leading to Dose Delays or Reductions of Any Study Drug
- Leading to Dose Delays or Reductions of Danvatirsen
- Leading to Death
- Leading to Death Related to Any Study Drug
- Toxicity Grade 3 or Higher
- By Maximum Toxicity Grade

An overall TEAE summary table will be provided separately, tabulating the number of subjects and events for any adverse event for the above categories. The following summaries will also be provided.

- Listing of Serious TEAEs
- Listing AEs Leading of Deaths
- TEAE by Preferred Term
- TEAE Related to Any Study Drug by Preferred Term

QMD Ref: Worldwide-TMP-ST-054-1.0_Effective: 12Aug2022	Governing QMD: Worldwide-SOP-ST-026
Confidentiality Statement	

This document is the property of Worldwide Clinical Trials Inc. and may not be duplicated, copied, altered or removed from company without prior approval from Worldwide Quality Assurance or in compliance with Worldwide Standard Operating Procedures.

Worldwide Clinical Trials Controlled Quality Management Document		
 WORLDWIDE CLINICAL TRIALS	Sponsor:	Flamingo Therapeutics
	Protocol Number:	FLM-6774-201
STATISTICAL ANALYSIS PLAN		

All adverse events will be listed. Listings of AEs leading to death will include a flag for on-treatment deaths. An on-treatment death is defined as death occurring from date of first dose of any study drug to 30 days after last dose of Danvatirsen or 90 days after last dose of Pembrolizumab, whichever is later.

Adverse event incidence is counted only once per system organ class and once per preferred per patient term. The number and percent of patients experiencing events are reported. Outputs reported at maximum severity show the highest severity reported by a patient per system organ class and preferred term. TEAE tables for system organ class, preferred term will be presented in alphabetically order to SOC and decreasing order of frequency for PT based on the Overall column.

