3.2 Definition of End of Study

A patient is considered to have completed the study upon completion of the last scheduled procedure shown in the Schedule of Activities (SoA) (Section 8.1), including the survival follow-up.

End of study is defined as the date of the last visit of the last patient.

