3.3 Duration of Study Participation

Study participation includes the screening, treatment, and follow-up periods. The screening period is 28 days. After randomization, patients receive treatment in 21-day cycles. The maximum duration of treatment with pembrolizumab is 24 months; there will be no limit of the duration of treatment with danvatirsen.

The follow-up period includes safety follow-up until 30 days (+7 days) after the last dose of study treatment, follow-up for AEs until 90 days (+7 days) after the last dose of pembrolizumab, and survival follow-up every 12 weeks (± 7 days) until death or withdrawal of consent, whichever occurs first. Survival follow-up will continue until at least 15 months after the last patient is randomized in the study.

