7.9.6 Reporting of Adverse Events and Serious Adverse Events

Patients will be monitored for all AEs from the time the first dose of study treatment is administered through 30 days after the last dose of study treatment and 90 days after the last dose of pembrolizumab. All AEs/SAEs occurring through the reporting period (30 days after last dose of danvatirsen or 90 days after last dose of pembrolizumab, whichever is longer) or until the time the patient begins a new anticancer treatment are reported in the CRF irrespective of causality. All AEs and SAEs that occur from the signing of the ICF until the first dose of study treatment should be recorded in the eCRF only if the event was related to a study procedure.

All patients with treatment-related AEs/SAEs should be observed until resolution or stabilization of the event. Any SAE occurring after the reporting period must be promptly reported if a causal relationship to the study treatment(s) is suspected.

Elective or previously scheduled hospitalizations for pre-existing conditions that have not worsened after initiation of treatment should not be classified as SAEs. For example, an admission for a previously scheduled ventral hernia repair would not be classified as an SAE.

All AEs should be recorded individually unless, in the opinion of the Investigator, the AEs constitute components of a recognized condition, disease, or syndrome. In the latter case, the condition, disease, or syndrome should be reported rather than each individual sign or symptom. If a constellation of signs and/or symptoms cannot be medically characterized as a single diagnosis or syndrome at the time of reporting, each individual event should be recorded as an AE or SAE, as appropriate, on the relevant form(s) (SAE Report Form and/or AE form). If a diagnosis is subsequently established, it should be reported as follow-up information becomes available. If a diagnosis is determined after the reporting of the constellation of symptoms, the signs/symptoms should be updated to reflect the diagnosis.

In general, disease progression should not be reported as an AE (or an SAE) or cause of death in this study. Instead, the AEs (or SAEs) considered as complications of disease progression should be reported. However, if no specific complications of disease progression can be identified that explain the clinical observations, “disease progression” may be reported as an SAE or cause of death.

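### The SAP's treatment-emergent window runs to the end of survival follow-up, beyond the protocol's all-cause AE collection, so TEAE tables could mix fully ascertained events with late SAEs reported only on open-label suspicion

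*SAP*

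**What the plan says.** SAP 5.13.1 states that TEAEs are reported as the protocol sets out. It then covers events starting on or after first dose and pre-existing conditions that have "worsened on or after the first dose of study drug up to the subject completion of the study". Every TEAE table uses this one definition.

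Protocol 3.2 says a patient has "completed the study upon completion of the last scheduled procedure shown in the Schedule of Activities (SoA) (Section 8.1), including the survival follow-up". Protocol 3.3 gives the minimum length: "Survival follow-up will continue until at least 15 months after the last patient is randomized in the study".

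Protocol 7.9.6 sets the all-cause reporting period at "30 days after last dose of danvatirsen or 90 days after last dose of pembrolizumab, whichever is longer", and closes it sooner for a patient who starts another anticancer therapy. For the time after that it says: "Any SAE occurring after the reporting period must be promptly reported if a causal relationship to the study treatment(s) is suspected". Protocol 7.6.3 describes the survival contacts as gathering survival status and new anticancer treatment; adverse events are not mentioned.

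Protocol 9.6 defines a TEAE by its start relative to first dose and gives no end. SAP 5.13.1 does apply a bound, "30 days after last dose of Danvatirsen or 90 days after last dose of Pembrolizumab, whichever is later", but only to flag on-treatment deaths in a listing.

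**The concern.** An incidence table is interpretable when every patient's events are sought by the same rule throughout the counting window. Here the window has two parts. In the first, all events are recorded whatever their cause. In the second, an event must be reported only if it is serious and an investigator who knows the treatment suspects a link to it.

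That second rule need not act alike in the two arms. Protocol 7.9.4 asks for a causality judgement on each study treatment. A combination patient has two candidate drugs, one of them investigational; a control patient has one. Part of the later period may also be spent on non-study therapy. What is at stake is whether the between-arm percentages, chiefly for serious, related, Grade 3 or higher and fatal TEAEs, describe one consistently observed period.

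**Working it through.** The plan states no figure to reproduce. The check compares the texts, followed by one hand calculation of calendar time.

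**Step 1: end of the counting window.** SAP 5.13.1 ends it at subject completion; Protocol 3.2 places survival follow-up inside completion. The window therefore reaches to the end of survival follow-up. If the end date in the SAP sentence is read as applying only to worsening conditions, new-onset events have no end date at all, so that reading does not close the gap.

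**Step 2: end of all-cause collection.** Under Protocol 7.9.6 this is the later of 30 days after danvatirsen and 90 days after pembrolizumab, cut short by new anticancer treatment. Footnote i of the Schedule of Activities agrees in substance.

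**Step 3: what can enter between the two.**

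| | Up to the end of the 7.9.6 period | After it, to study completion |
|---|---|---|
| AEs required | All, regardless of cause | None that are non-serious |
| SAEs required | All, regardless of cause | Only if suspected related |
| Causality judgement | Recorded, but does not decide entry | Decides entry; open-label |
| Counted as TEAE by SAP 5.13.1 | Yes | Yes, if reported |

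Protocol 7.9.6 routes SAE notifications through the AE form in the EDC system, so late reports can reach the data set from which the tables are built.

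**Step 4: does another passage repair it?** The reference to the protocol does not, because Protocol 9.6 has no end date. The 30/90-day bound in SAP 5.13.1 does not either: it serves the death flag only, and the tables of TEAEs leading to death carry no such limit.

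**Step 5: calendar length of the gap (illustration).** Inputs: the 15-month minimum (Protocol 3.3), taken from the patient's own randomization; 90 days after pembrolizumab (Protocol 7.9.6); 30.4375 days per month (SAP conversion factor). Assumptions: the month of last pembrolizumab dose, the 90-day limit governs, the patient is still followed at 15 months, and no new therapy starts before day 90.

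Gap = 15 − month of last dose − 90/30.4375 = 15 − month of last dose − 2.96

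| Last pembrolizumab dose (assumed month) | Gap (months) |
|---|---|
| 2 | 10.0 |
| 3 | 9.0 |
| 6 | 6.0 |
| 9 | 3.0 |

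The gap is longer if new therapy starts earlier or the patient was randomized before the last one. These are months of calendar time, not counts of events.

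**The case against.** The strongest reply is that the SAP breaks no protocol TEAE rule, because Protocol 9.6 sets no end date and the 30/90-day limit is a collection rule. This is right as far as it goes: the mismatch is between the SAP's counting window and the protocol's collection period, not between two TEAE definitions. It does not remove the problem, since the SAP had to choose an end and chose one that data collection does not support.

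A second reply is that collection itself restricts what can enter, the summaries are descriptive with no between-arm safety test specified, all AEs are listed, and the study is ending early. This stands, and it limits the impact.

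Four stronger readings are tempting, and the documents do not support them:

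- **AE collection stops at the end of the period.** It does not; suspected-related SAEs are still reportable, and that exception is what makes late entry selective.
- **The rule inflates toxicity in the combination arm.** Two candidate drugs could raise suspicion there, but if control patients stop treatment sooner, they would have more time after the period. Pembrolizumab is in both arms, so late related SAEs can arise in either. The net direction is unknown.
- **The share of the window outside collection measures the bias.** It measures time in which little is required to be reported. Dividing an all-patient mean window by the follow-up of a long survivor would also mix two different groups.
- **Continued follow-up of ongoing AEs (Protocol 7.6.1) adds cases.** SAP 5.13.1 counts a patient once per term, so this can at most change a maximum grade.

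**Conclusion.** The point holds as a mismatch between the SAP's TEAE window and the protocol's all-cause collection period. It leaves room for late events, selected on seriousness and open-label causal suspicion, to enter tables otherwise built on complete ascertainment, and that selection could differ by arm. The text alone establishes this; the Step 5 illustration is not needed for it.

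The practical effect is probably small. Neither the number nor the direction of late events follows from the documents, and the early termination recorded in SAP Section 9 may shorten the gap, so the planned 15-month minimum cannot be assumed for the actual analysis. The change is still worth making because it is cheap and the same SAP section already uses the 30/90-day boundary.

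**What to change.** In SAP 5.13.1, define a TEAE as an event with onset or worsening from first dose through the end of the Protocol 7.9.6 reporting period (30 days after the last danvatirsen dose or 90 days after the last pembrolizumab dose, whichever is later), or through the day before new anticancer therapy if that is earlier. Apply this to every TEAE table in both arms. Show SAEs reported after the window as suspected-related by arm, in a separate row and listing, so that no late toxicity drops out of the report.

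The cost is one sentence, a date condition in the programs, and one added row and listing. Dosing and the start of new anticancer therapy are already recorded (Protocol 5.3, 7.4 and 7.6.3). SAP Section 5 allows amendment before database lock; after lock, the change belongs in the addendum that section describes.

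There are two downsides. Late related SAEs no longer count in the main TEAE percentages, which is why the separate row is essential. The change also does not equalize observation time: if treatment lasts longer in one arm, the windows still differ in length.
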